6.4 Receiving, dispensing and accounting of the IP

The IP for the study will be transported to the Research Center accompanied by an invoice and a shipping form, which should contain all the necessary information to fill in the receipt form and check by the Research Center. If the quantity of the medication sent is inconsistent with the quantity described on its shipping invoice or form, or if the product is damaged in any way, the sponsor must be immediately contacted, and the products segregated until a favorable opinion is issued by the sponsor.

A designated pharmacist from the Research Center will be responsible for both receiving and storing the study medications, as well as dispensing, collecting, and accounting for those dispensed to research participants, through the completion of the IP Dispensing and Return Control Form provided by the Sponsor. In case of discrepancies, these must be properly documented in a specific field of the form, as well as the reason why they occurred. The dispensing of study medications will be carried out in sufficient quantities, as allocated in the research.

During monitoring visits, checks will be made between the information contained in the dispensing and control forms and the physical quantity of study medications. All medications used or unused, as well as empty packaging, during the study must be returned to the Sponsor at the end of the study to be destroyed in accordance with current legislation.

6.5 Investigational Product application procedure

At visit V0, prior to the application of PSI, an analysis of the genital area and registration of vital signs should be done. The genital area should be washed beforehand with water and neutral soap, followed by drying. The IP should be applied with gloves on the entire surface of the genital organ: from the glans to the base of the penis in the case of men, and on the clitoris and labia majora in the case of women.

The application will be performed by a trained nursing professional. The characteristics of irritation and sensitivity on the applied skin (AE of the formulation on the skin) will be observed and recorded from this moment on.

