| Study Identification | BZ371CLI003 |
| Study description | Single dose, single center, non-blinded |
| Dosage and Administration | BZ371A, at a concentration of 5 mg/mL, applied to the genital area (entire penis including glans, clitoris, labia majora and minora) in a volume of 1.5 mL. The genital area should be washed with water and mild soap beforehand, followed by drying. The product should be applied using gloves. |
| Objectives | 
 • Determine safety and tolerability of BZ371A when topically Applied to genitália of healthy men and women • Evaluate systemic presence of BZ371A, or its fragments, through a pharmacokinetics study using blood, when BZ371A is topically applied. |
| Outcomes | 
 • Safety 
 ○ Adverse Events Report ○ Physical Exam in the genital region ○ Vital signs, including heart rate and systolic blood pressure ○ Electrocardiogram (ECG) ○ Laboratorial Exam, including (i) complete blood count, including platelets; (ii) coagulation profile, including prothrombin time (PT) and activated partial thromboplastin time (aPTT); (iii) biochemistry, including glucose, sodium, potassium, urea, creatinine, chloride, total calcium, phosphorus, total proteins and fractions (albumin and globulin), aspartate aminotransferase (AST), alanine aminotransferase (ALT), alkaline phosphatase, gamma-glutamyl transferase (GGT), total cholesterol, HDL cholesterol, triglycerides, pH; (iv) urinalysis for abnormal elements and sediment (AES). • PK analysis 
 ○ Detection of BZ371A and its fragments in the blood at the following collection times: pre-dose, 15, 30, 60, 180, and 360 minutes. ○ If detected, determine the pharmacokinetic parameters: maximum concentration (Cmax), half-life (t_{1/2}), area under the curve (AUC), clearance (CL), distribution volume (Vd). |

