2. STUDY GOALS

2.1 Primary goals

The objectives of this study are:

- To determine the safety and tolerability of BZ371A when topically applied to the genitals of men and women;

- To determine the systemic presence of BZ371A and/or its fragments, through a pharmacokinetic study in the blood, when topically applied to the genitalia of men and women.

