3. STUDY PLAN

3.1 General study design

Open-label study, conducted at a single center, with the aim of being the first human trial with the new BZ371A formulation in order to guide future clinical studies such as to understand safety, tolerability, and systemic bioavailability of the peptide topically applied.

The study will comprise only one group, consisting of 6 men and 6 women.

The formulation will be administered in a single dose, topically, followed by medical and laboratory analyses for safety assessment, and blood collections for pharmacokinetic analysis.

The concentration of BZ371A and its fragments in the blood will be measured by an appropriate analytical method, developed for this purpose and previously validated. The collected blood will be

analyzed by the company *Unidade Integrada de Farmacologia e Gastroenterologia* (UNIFAG), the same company that validated the analytical method, and will not be stored or used for any other purpose.

The visits and procedures are illustrated in the table below:

CHART 1. VISITS AND BZ371CLI003 STUDY PROCEDURES

| Visit | V-1 | V0 | V1 |
|--|-----------|-----------------------|-----------------|
| Day | D-1 | D0 | D7 |
| Interval | -7 a 0 | 0 | +2 a -2 |
| Visit Name | Screening | PK | Safety revision |
| ICF | X | | |
| Demographic data | X | | |
| Medical history | X | X | |
| Physical exam | X | | X |
| Genitalia exam | X | X / X ^(*) | X |
| Anthropometric data | X | | |
| Vital Signs | X | X / X ^(**) | X |
| Concomitant medication | X | X | X |
| Blood collection for laboratory analysis | X | X ^(*) | |
| Urine collection | X | X ^(*) | |
| Electrocardiogram | X | X ^(*) | X |
| Eligibility | X | X | |
| Blood sample collection for PK | | X | |
| BZ371A application | | X | |
| AE collection | | X | X |
| Next visit scheduling | X | X | |
| Study dismissal | | | X |

^{*}: after 360 minutes after IP application

^{**}: after IP application at 30, 60, 180 and 360

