3.2 Study location

The study will be conducted at a single center, at the headquarters of Azidus Brasil Pesquisa Científica e Desenvolvimento, located in the city of Valinhos. Azidus Brasil is a Clinical Research Center that has a highly qualified team with 20 years of experience in developing drugs and health products. It has certified and equipped units for conducting Phase I clinical research studies. Participants will receive specialized assistance and care throughout the treatment period of this protocol.

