In order to be completed, physical examination must be performed at V-1 and V1 to capture diseases and AEs, respectively. The assessment includes a general inspection (skin, oropharynx, and appendages), and cardiovascular, pulmonary, digestive, musculoskeletal, peripheral, and neurological exams.

Physical examination of the male or female genitalia must be performed at all visits: at V-1, for eligibility assessment; at V0, before and 360 minutes after IP administration, for AE assessment; and at V1, for AE assessment.

5.2.4 *Blood and urine sample collection*

In order to evaluate the systemic safety of the PSI, blood and urine will be collected before (at V-1) and after the application of the IP (at V0 at the 360-minute time point), for analysis of the following laboratory tests: (i) complete blood count, including platelets; (ii) coagulogram, including PT and PTT; (iii) biochemistry, including glucose, sodium, potassium, urea, creatinine, chloride, total calcium, phosphorus, total and fractionated proteins (albumin and globulin), TGO, or AST, TGP or ALT, alkaline phosphatase, gamma GT, total cholesterol, HDL cholesterol, triglycerides, pH; (iv) urinalysis.

In addition, blood will be collected from women during the V-1 visit for the β -HCG test and confirmation of absence of pregnancy, allowing the participant to be included in the study.

Approximately 20 ml of blood will be collected per evaluation (V-1 and V0), totaling 40 ml of blood for laboratory tests.

Any difference between the baseline and post-application of the IP should be evaluated by the examiner and, if clinically significant, should be noted as an AE.

5.2.5 *Electrocardiogram*

In order to evaluate the cardiac safety of PSI, an ECG examination will be performed at all visits. At V0, it should be performed 360 minutes after the administration of PSI, with a window of +/- 30 minutes. At V-1 and V1, the cardiac evaluation can be performed concurrently with the clinical evaluation.

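### The synopsis and section 6.5 disagree on the female dosing sites: the section 6.5 list omits the labia minora.

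*Combined protocol and SAP*

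**What the plan says.** The synopsis, in its Dosage and Administration row, has the gel "applied to the genital area (entire penis including glans, clitoris, labia majora and minora) in a volume of 1.5 mL". The same row covers washing, drying and the use of gloves.

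Section 6.5, the section devoted to application, opens with a general instruction: "The IP should be applied with gloves on the entire surface of the genital organ". After a colon it gives the sites for each sex. For men the list runs from the glans to the base of the penis. For women the gel goes "on the clitoris and labia majora in the case of women". The section adds that "The application will be performed by a trained nursing professional" and that irritation and sensitivity of the treated skin are observed from the time of application.

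No other part of the documents lists the female application sites. Section 2.1 sets the goal: "To determine the safety and tolerability of BZ371A when topically applied to the genitals of men and women". Section 5.2.3 provides for local follow-up: "Physical examination of the male or female genitalia must be performed at all visits".

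**The concern.** A dosing instruction should name the same tissue wherever it appears. Here the synopsis names three female sites and the section 6.5 list names two. Section 6.5 is also at odds with itself for women, because its opening calls for full coverage and its list stops short of that.

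What is at stake is local tolerability in women. Local reactions such as itching, redness, urticaria, rash and swelling are listed as possible effects in section 7.2, and section 3.1 describes this as the first human trial of the new formulation, meant to guide later studies. If the labia minora were not dosed, a normal examination of that tissue would say nothing about how it tolerates the gel. A report based on the synopsis could then claim tolerability at a site that was never treated. Section 8.8 also requires procedures to be followed in full and deviations to be described and justified. With two different lists, it is unclear which application complies.

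**Working it through.** The check is mainly a comparison of texts.

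**Sites, side by side**

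| Text | Men | Women |
|---|---|---|
| Synopsis, Dosage and Administration | Entire penis, glans included | Clitoris, labia majora, labia minora |
| Section 6.5, opening instruction | Whole surface of the organ | Whole surface of the organ |
| Section 6.5, list after the colon | Glans to base of penis | Clitoris, labia majora |

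For men, all three rows describe the same coverage. For women, the first two rows agree and the third is shorter by one site. The male list shows that the words after the colon were meant to spell out full coverage, which suggests that the female list was meant to do so too and lost an item.

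**Dose**

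Inputs: concentration 5 mg/mL and volume 1.5 mL (synopsis; section 6.1, Chart 2). Neither depends on sex or on the area covered.

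Dose = 5 mg/mL x 1.5 mL = 7.5 mg under either reading.

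**Examinations that bear on the point**

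Inputs: 6 women (section 3.1: "The study will comprise only one group, consisting of 6 men and 6 women") and two scheduled genital examinations after dosing, at 360 minutes on V0 and at V1 (Chart 1; section 5.2.3).

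Post-dose female examinations = 6 x 2 = 12.

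- If the labia minora are dosed, all 12 can inform tolerability there, because section 5.2.3 does not restrict the examination to particular sub-sites.
- If the section 6.5 list is followed alone, none of the 12 can, and neither can the observation that starts at application, since that concerns treated skin.

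The two readings therefore differ only in which tissue is treated. The amount given and the examination schedule are the same.

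**The case against.** The strongest reply is that the document resolves the matter itself. The full-coverage instruction in section 6.5 is as literal as the list, and leaving out the labia minora would breach it. The synopsis also gives application steps and names that tissue, so staff have a complete text to hand. No passage excludes the labia minora or gives a reason to. The English shows signs of translation, and the working-language text may already be correct. Finally, no sub-site endpoint is planned: section 2.2 asks for a local examination of the genital area and section 9 treats adverse events qualitatively, so no planned estimate is lost.

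Most of this stands. It makes inclusion the likelier intention and keeps the point small. It does not remove the disagreement, because the female list still falls short of both its own opening instruction and the synopsis, while the male list does not.

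A reader might go further and infer any of three things that the documents do not support:

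- **That the labia minora will in fact go undosed.** That follows only if the list is treated as exhaustive and as overriding the words before it.
- **That coverage will vary from woman to woman.** Section 3.2 says "The study will be conducted at a single center" and a trained nurse applies the gel; nothing points to variation.
- **That absorption or the pharmacokinetic results are compromised.** The dose is fixed, and the documents give no figure linking absorption to the site or area of application.

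**Conclusion.** The point holds as a minor inconsistency in a dosing instruction. It is certain that the two female site lists differ. It is unlikely, though possible, that the labia minora would be left untreated as a result.

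In the worst case, local tolerability of that one tissue would be untested in all 6 women. The validity of the adverse event, vital-sign, ECG, laboratory and pharmacokinetic data is not in question. The worst case assumes that the nurse works from the section 6.5 list alone, and that the site's working text has the same wording as the English. The documents do not settle the second assumption.

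**What to change.** Amend the female site list in section 6.5 to name the clitoris, labia majora and labia minora, so that it matches the synopsis and the section's own opening instruction. If the working-language protocol already says this, correct only the English text.

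If exclusion is intended, delete the labia minora from the synopsis, reconcile the full-coverage wording in section 6.5, and limit the local tolerability conclusion for women to the treated sites.

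A field in the case report form for the sites covered would be useful but is not needed.

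The cost is one phrase in the protocol, approved through the usual change process. No visits, procedures or data are added.

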7. SAFETY

7.1 AE definition

An AE is defined as "any unfavorable medical occurrence in a patient, or clinical trial participant, to whom a pharmaceutical product has been administered, which does not necessarily have a causal relationship with the treatment." All AEs observed after the signing of the ICF, regardless of the possible causal relationship with the investigational product, must be reported on the AE page(s) of each individual participant's CRF. AEs can be considered as the following:

- Suspected adverse drug reactions (SADRs);
- AEs due to medication's quality deviations;
- AEs due to unapproved use of medication;
- Medication interactions;
- Therapeutic ineffectiveness, total or partial;
- Medication-related intoxications;
- Medication abuse;
- Potential and actual medication errors.

If the research participant has a relevant previous medical history, the Investigator must specify in the participant's individual CRF the date of diagnosis, history of follow-up, and the treatment followed. Pre-existing conditions will not be considered as AE, except when there is/are:

- Decompensation of the controlled chronic disease before starting the clinical study;
- Symptoms Increased frequency or intensity of symptoms of the disease described in the medical history related to the use of the study medication;
- Need for discordant treatment compared to the treatment usually used for the disease described in the medical history;
- Specified in the clinical study protocol.

The following will not be considered AE:

- Planned elective procedures before the start of the clinical study, even when performed during its duration, except for any complications that occur during the procedure.

The Sponsor will be responsible for all expenses related to examination procedures, especially those for diagnosis, treatment, hospitalization of the participant, and other necessary actions for the resolution of AEs related to the clinical trial (Art. 12, ANVISA RDC 09/2015).

The safety of treatments will be evaluated throughout the study by the incidence and classification of AEs occurring between treatments in terms of type, frequency, and intensity.

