7.6 AE classification according to causality

To determine causality, the Investigator should use the World Health Organization's (modified) system. In this way, three criteria will be evaluated to define the causal relationship:

- Temporal relationship - The AE occurred after the use of the investigational product (IP), within at least 10 times its half-life;
- Other causes - Strong presence of other causes that may be related to the AE;
- Known effect - The effect is known or physiologically related to any of the components of the IP.

CHART 5. MONITORING OF THE IP THROUGHOUT THE STUDY

| Classification | Time related | Other causes | Known effect |
|----------------|--------------|--------------|--------------|
| Improbable | No | NA | NA |
| | Yes | Yes | No |
| Possible | Yes | No | No |
| | Yes | Yes | Yes |
| Probable | Yes | No | Yes |

- Probable: a reaction that follows a reasonable temporal sequence between medication administration and the appearance of the AE. It follows a known pattern of response to the suspected medication. It cannot be reasonably explained by the participant's known clinical state characteristics.

- Possible: a reaction that follows a reasonable temporal sequence between medication administration and the appearance of the AE. It follows a known pattern of response to the suspected medication, but it could have been produced by the participant's clinical state or other therapies administered concomitantly.
- Unlikely: a reaction that does not follow a reasonable temporal sequence between medication administration and the appearance of the AE; or that does not follow a known pattern of response to the IP, and can be explained by the participant's known clinical state characteristics.

If there is not enough data available to correctly establish the causality of the AE (due to insufficient evidence, conflicting data, or poor documentation), the Investigator should classify it as **non-evaluable**.

AEs classified as "Probable" and "Possible" will be considered "related" to the PSI, and those classified as "Unlikely" will be considered "not related".

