9. STATISTICAL ANALYSIS PLAN

The statistical analyses will aim to describe the pharmacokinetic parameters. Adverse events (AEs) will be analyzed qualitatively. Therefore, every detected adverse event will be described in the results, characterized by: (i) identification, if possible, as a medical entity (sign, symptom, or disease); (ii) intensity (mild, moderate, or severe); (iii) severity, whether it is a serious adverse event (resulting in death, abortion, immediate risk of death, hospitalization or prolongation of hospitalization, or disability); (iv)

duration; (v) resolution (complete, partial, or unresolved); (vi) mode of resolution (spontaneous or requiring medicinal treatment); and (vii) causality with the investigational product (IP).

Participants in whom the IP has been administered will be included in the analysis.

A sample size of 12 participants is considered adequate for a pharmacokinetic curve.

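### The second exception in Section 7.1 requires relatedness to the study drug before worsening symptoms of a pre-existing disease count as an AE, against that section's own causality-free reporting rule

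*Combined protocol and SAP*

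**What the plan says.** Section 7.1 opens with an AE definition that does not require a causal link to treatment. It then gives the recording rule: AEs observed after the consent form is signed, "regardless of the possible causal relationship with the investigational product, must be reported" on the AE pages of the CRF.

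Next comes a default for medical history: "Pre-existing conditions will not be considered as AE, except when there is/are" one of four situations:

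1. "Decompensation of the controlled chronic disease before starting the clinical study"
2. "Increased frequency or intensity of symptoms of the disease described in the medical history related to the use of the study medication"
3. "Need for discordant treatment compared to the treatment usually used for the disease described in the medical history"
4. "Specified in the clinical study protocol"

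Only the second carries a relatedness condition.

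Later sections place causality after recording. In Section 7.6, "three criteria will be evaluated to define the causal relationship" for an AE. Section 9 says that "every detected adverse event will be described in the results" and lists causality as the last of seven descriptors. Section 2.1 names safety and tolerability as a primary goal.

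**The concern.** An AE record is meant to be collected first and attributed second. If attribution decides whether an event enters the record, the events dropped are those the investigator thought unrelated. They are then not graded under Chart 5 and not described under Section 9. Here that judgement is made in an open-label, single-arm study of 12 people, with no control group against which a shortfall would show. Section 3.1 describes the study as the first human trial of the new formulation, so effects not yet known for the product are among the things it should be able to detect.

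**Working it through.** The documents give no AE rate, error level or power tied to this clause, so there is no plan figure to reproduce. The check is a comparison of clauses, followed by a scale illustration.

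**Step 1. Which events does the condition reach?**

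| Event | Route into the AE record | Relatedness needed? |
|---|---|---|
| New-onset event | 7.1, general definition | No |
| Hypotension by the stated thresholds | 5.2.2 | No |
| Clinically significant laboratory change | 5.2.4 | No |
| Decompensation of a controlled chronic disease | 7.1, exception 1 | No |
| Worsening that needs discordant treatment | 7.1, exception 3 | No |
| Event specified in the protocol | 7.1, exception 4 | No |
| Any other increase in frequency or intensity of symptoms of a disease in the history | 7.1, exception 2 | **Yes** |

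Only the last row is affected. For that row the general reporting rule is no cure: it governs what is done with AEs, while the exception decides whether the event is one.

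**Step 2. What would be dropped inside that row?** Section 7.1 does not say how relatedness is to be judged at this step. Suppose the 7.6 criteria are used, and assume that the pre-existing disease counts as another cause. Section 7.6 counts Probable and Possible as related and Unlikely as not related. I read Chart 5's Improbable as the text's Unlikely.

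| Time related | Other cause | Known effect | Chart 5 grade | Related? | AE under exception 2? |
|---|---|---|---|---|---|
| Yes | Yes | Yes | Possible | Yes | Yes |
| Yes | Yes | No | Improbable | No | **No** |
| No | – | – | Improbable | No | **No** |

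The second line is the case that matters most: worsening after dosing, of a kind not yet known for the product, in someone whose disease offers an alternative explanation. The third line includes any worsening between consent and application. It cannot be related to a product not yet given, so exception 2 can never admit it, although the recording rule starts at consent.

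If relatedness is instead judged informally at first sight, even a first-line event could be dropped.

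**Step 3. Direction.** The condition can remove events from the record and cannot add any. The effect is therefore zero or towards fewer AEs.

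**Step 4. Scale, with assumed counts.** One participant is 1/12 = 8.3 percentage points. Exact two-sided 95% (Clopper-Pearson) limits are:

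- 0/12: 0% (0 to 26.5%), upper limit 1 − 0.025^(1/12) = 0.265
- 1/12: 8.3% (0.2 to 38.5%), lower limit 1 − 0.975^(1/12) = 0.002, upper limit the 97.5% point of Beta(2, 11) = 0.385
- 2/12: 16.7% (2.1 to 48.4%)

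These show what any single missed participant does at n = 12. They do not measure this clause, and Section 9 plans no interval.

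**The case against.** The strongest reply is that the protocol's other rules close most of the gap. Three of the four exceptions need no relatedness. Headache, pruritus and diarrhea are in Table 1 as expected events that are actively sought, so they arguably fall under exception 4. A time-related worsening of any of them grades as Possible under Chart 5, hence related, and so satisfies exception 2 itself. Section 7.9 has symptoms monitored whether or not related. Participants are healthy, the exclusions in 4.1.2 remove many relevant diseases, there is one dose, and the last visit is at D7. The bullet is also visibly garbled, possibly from translation.

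Much of this stands, and it rules out some stronger readings:

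- A reader might infer that any worsening of a pre-existing condition must be drug-related to count. Step 1 shows that this is too broad.
- A reader might infer that the primary safety result is biased towards a clean profile. The documents give no rate of pre-existing disease or of its worsening, so a bias is possible in one direction but not shown.
- A reader might infer that a dropped event is lost for good. Section 7.9 provides for monitoring and a follow-up report to the sponsor, so some trace may exist, though not as an AE.

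The objection does not remove the contradiction. Section 7.1 does not invoke 7.6, so Chart 5 cannot be relied on at this step. Where it is used, it still drops effects not known for the product. Whether Table 1 events count as protocol-specified is left to the reader. Monitoring a symptom under 7.9 does not make it an AE. Healthy status does not exclude all history, since 7.1 itself provides for controlled chronic disease. The garbling offers no harmless reading: a disease already in the history cannot be drug-related, so the phrase must qualify the worsening.

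**Conclusion.** The second exception in 7.1 is wrong as written. It contradicts the definition and the reporting rule in its own section, and it puts a causality judgement before the recording that 7.6 and Section 9 assume has already happened. The gap is limited to symptomatic worsening of a disease in the medical history that is not decompensation, does not need discordant treatment and is not otherwise specified in the protocol. Within it, worsening judged unrelated could go unrecorded, most clearly when the effect is not yet known for the product and the disease supplies another cause.

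Any effect is towards fewer AEs. The size cannot be computed and may be small, and the 8.3 points per participant is an illustration only. The conclusion rests on the natural reading of the bullet. The detail of which events would drop also assumes that the existing disease is counted as another cause.

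**What to change.** Delete the closing phrase of the second exception that ties it to the study drug. Add an instruction that any increase in frequency or intensity of symptoms of a pre-existing disease after ICF signature, compared with the state recorded at V-1, is entered as an AE. For events after application, the V0 pre-dose state is the reference. Causality is then assessed under 7.6. The instruction should not be limited to worsening after application, because that would conflict with the rule in 7.1 that reporting starts at consent.

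The comparison needs a note of baseline symptom frequency and intensity. This can go with the medical history that Chart 1 already schedules at V-1 and V0.

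The cost is one deleted phrase, a short CRF instruction and that baseline note. The AE count may be slightly higher. The change should be in place before data collection, because events never entered as AEs may not be recoverable afterwards.
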